### **8.3.13 Concomitant Medications**

Concomitant medication information will be collected and documented at each scheduled clinic visit. Any concomitant drugs (prescribed or over-the-counter, which include vitamin and herbal supplements) used during the course of the study and the reason for their use will be recorded. Information regarding the timing, type, and amount will be recorded in an eCRF. Excluded drug therapies to consider during screening are listed in the exclusion criteria in Section [4.3](#).

### 8.3.14 [REDACTED]

### 8.3.15 MNREAD

Standard MNREAD Acuity Charts will be used to assess Reading Acuity, Critical Print Size, Maximum Reading Speed, and Reading Accessibility Index.

Reading speed is a strong predictor of visual ability and vision-related quality of life for patients with vision loss ([Hazel 2000](#)). For this reason, reading performance has been used as an outcome measure in clinical trials for judging the effectiveness of treatments ([Mahmood 2015](#)).

The Reading Accessibility Index summarizes an individual's access to text over the range of print sizes found in everyday life. The Reading Accessibility Index relies on a simple calculation: averaging the reading speed measured over the 10 largest print sizes on the MNREAD and normalizing it by the mean value for a group of normally sighted young adults ([Calabrese 2016](#)). The Reading Accessibility Index is a single-valued measure that depends on both the range of accessible print sizes for a subject, and the subject's speed of reading within this range. Because the Reading Accessibility Index is normalized by the value for a group of normally sighted young adults (aged 18–39 years), a Reading Accessibility Index of 1.0 represents normal performance for this age group. Values less than 1.0 mean reduced accessibility to printed text within the range of print size encountered in daily life ([Calabrese 2016](#)).

The MNREAD Acuity Charts are continuous-text reading-acuity charts suitable for measuring reading acuity and reading speed of normal and low-vision patients. The study manual should be referenced for detailed instructions.

The reading level of the MNREAD Acuity Charts is approximately 2nd to 3rd grade level. It is estimated that subjects around the age of 8 years or older will be able to complete this assessment. Any subject less than the age of 8 years old will not be required to have this study assessment administered.

Three charts will be utilized for the MNREAD testing; one chart will be used for OD, one chart for OS, and the third chart for OU. It is imperative that the charts used for the monocular and binocular testing be changed out to decrease the likelihood of memorization of the text sentences by the subject.

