## 3 STUDY OBJECTIVES AND ENDPOINTS

### 3.1 Objectives

#### 3.1.1 Primary Objective

The primary objective of this study is to evaluate the effect of ataluren on Maximum Reading Speed as measured using the Minnesota Low Vision Reading Test (MNREAD) Acuity Charts in subjects with nonsense mutation aniridia.

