## 11 STATISTICS

### 11.1 Sample Size

The study is planned to enroll a minimum of 36 subjects with nonsense mutation aniridia who are  $\geq 2$  years of age. This number of subjects should provide adequate information to evaluate the safety of ataluren in this population. For a statistical hypothesis test for any efficacy endpoint, the study will have 60% power to detect an effect size (i.e., standardized mean difference) of 0.85, or 80% power to detect an effect size of 1.06, at the 0.05 significance level (two-sided).

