2.4 Study Design

This is a Phase 2, multicenter, stratified, randomized, double-masked, placebo-controlled study with a 4-week screening period, a 144-week treatment period, an optional 96-week open label sub-study, and a 4-week post-treatment follow-up period (either study completion or early termination). A minimum of 36 subjects with nonsense mutation aniridia who are ≥ 2 years of age are planned for enrollment into this study at investigator sites in US and Canada.

During the 4-week screening period, subjects will be assessed for eligibility.

Eligible subjects will enter the 144-week treatment period consisting of two stages:

- Stage 1 (Weeks 1 to 48) during which subjects will receive either ataluren or placebo in a masked fashion;
- Stage 2 (Weeks 49 to 144) during which subjects will receive open-label ataluren.

Eligible subjects will be randomized in a masked 2:1 fashion to either ataluren or placebo. Randomization will be stratified by age: ≤ 10 years versus > 10 years. Masked study drug will be dosed three times a day: 10 mg/kg in the morning, 10 mg/kg at midday, and 20 mg/kg in the evening for 48 weeks. Subjects (or parent/legal guardian) will record each dose on a diary card provided by PTC Therapeutics.

After completion of the Stage 1 (Week 48), subjects will be eligible for an additional 96 weeks of open-label ataluren treatment. Subjects who received ataluren during Stage 1 will continue to receive ataluren; subjects who had been randomized to placebo will receive ataluren during Stage 2

There will be an optional sub-study at the end of the Stage 2 Open-Label Extension. Subjects will be able to consent to receive an additional 96 weeks of ataluren treatment, returning to the clinic every 24 weeks. The assessments to be conducted are outlined in the schedule of events. Subjects who choose not to participate in the sub-study will be required to complete the Post-treatment follow-up visit at the end of the Stage 2 Open-Label Extension.

[figure not shown]
The start of the sub-study will require prior approval of a protocol amendment from applicable Institutional Review Boards and will continue for 96 week or until commercial availability of ataluren for this indication, whichever is first, or until a positive risk-benefit assessment in this indication is not demonstrated.

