2.5 Sample Size

The study was planned to enroll a minimum of 36 subjects with nonsense mutation aniridia who are ≥ 2 years of age. This number of subjects has been reduced to 24 and should provide adequate information for an initial evaluation the efficacy safety of ataluren in this population.

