6.2 Intent-to-Treat Analysis Population

The intent-to-treat (ITT) population will include all randomized subjects who receive at least 1 dose of study drug. Subjects will be analyzed as randomized. The ITT population will be the primary efficacy population.

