10 MISSING DATA HANDLING

10.1 Handling Missing Efficacy Data

Missing data for the primary efficacy endpoint will be imputed through Week 48 using last observation carried forward (LOCF) as the primary method of imputation for the efficacy and ITT analysis populations.

As a sensitivity analysis to the use of LOCF, multiple imputation (using SAS PROC MI and SAS PROC MIANALYZE) will also be used to impute missing endpoint data. Missing data at week 48 will be imputed for the primary endpoint for the ITT population only. Missing data predictors will be baseline MRS, MNREAD baseline parameters of reading acuity index, critical print size, reading acuity, and subject age. Twenty iterations will be generated with a prespecified seed number of 20191015 using the Markov Chain Monte Carlo (MCMC) method.

A second sensitivity analysis will be performed using a tipping point approach. The best and worst MRS change will be selected over the entire sample. These values will be rounded to one decimal places. All ataluren-treated subjects with missing endpoint data will be imputed with the worst value and all placebo treated subjects with missing endpoint data will be imputed with the best value and a p-value derived. Next, all ataluren-treated missing values will be replaced by the next worst value all placebo-treated missing data will be replaced by the next best value and a p-value derived. This process will be continued until all ataluren-treated missing data are replaced with the best value and all placebo-treated missing data are replaced by the worst value. The point at which the p-value “tips” from non-significance to significance will be noted relative to its order and number of analyses performed. In the event that all permutations are statistically significant, then it can be concluded that imputation does not result in a false positive.

Efficacy data will not be imputed for the open-label study period.

If any needed/permitted surgical treatment is performed during the study, and as a consequence, any assessment outcomes are affected significantly due to the surgical procedure, these assessment outcomes on and after the surgery will be set as missing and the last assessment prior to the surgery will be used for later assessment time points.

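### The SAP's multiple imputation and tipping-point rules cover the whole ITT set, including young children for whom MNREAD is not required, so both sensitivity analyses of the primary endpoint treat untested children as dropouts

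*Protocol*

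**What the plan says.** **Who is enrolled.** SAP 2.4: "A minimum of 36 subjects with nonsense mutation aniridia who are ≥ 2 years of age are planned for enrollment". SAP 2.5 later says: "This number of subjects has been reduced to 24". Protocol 4.2 sets the same lower age limit of 2.

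**Who is tested.** MNREAD supplies the primary endpoint, Maximum Reading Speed (MRS) with both eyes, and the first key secondary endpoint. Protocol 8.3.15 says: "Any subject less than the age of 8 years old will not be required to have this study assessment administered". Section 13.2.3.3 repeats this. Both sections present 8 as an estimate of when children can manage the charts. In Stage 1, MNREAD is scheduled only at Day 1 and Week 48 (SAP Appendix A, Table 1).

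**Who is analysed.** SAP 6.2 defines ITT as everyone randomised and dosed, with no condition on age or baseline, and adds: "The ITT population will be the primary efficacy population". The set that requires a baseline and a post-baseline value (SAP 6.3) is supportive only. SAP 7.7 names visual acuity, keratopathy and iris area for it, but not MNREAD.

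**How gaps are filled (SAP 10.1).** LOCF is the primary method. For multiple imputation: "Missing data at week 48 will be imputed for the primary endpoint for the ITT population only". For the tipping point: "All ataluren-treated subjects with missing endpoint data will be imputed with the worst value", with placebo subjects mirrored at the best value. No sentence treats a child who was never tested differently from a subject who left.

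**What is claimed.** The primary objective (Protocol 3.1.1) concerns the effect on reading speed "in subjects with nonsense mutation aniridia", with no reference to ability to take the test. Protocol 11.1 states power broadly: "For a statistical hypothesis test for any efficacy endpoint, the study will have 60% power" at an effect size of 0.85, and 80% at 1.06.

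**The concern.** A reading speed that was never measured because the child is too young to read the chart is not missing in the way that a dropout's value is missing. A rule that fills both alike makes the sensitivity analyses of the primary endpoint answer a different question: what happens if reading speeds are supplied for non-readers, instead of how robust the result is to loss of follow-up. The more young children enrolled, the less these analyses say about real dropout.

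The plan also names one population and in practice analyses another. The report could present an ITT result for the whole enrolled age range when it rests only on those who could do the test at Day 1. The stated power does not show how many that is.

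**Working it through.** **1. Apply each rule to a child with no MNREAD at Day 1 or Week 48.**

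| Step | What the child has | What happens |
|---|---|---|
| LOCF, percent change, ANCOVA (SAP 5, 7.7, 10.1) | Nothing to carry forward, no denominator, no baseline covariate | The row drops out and no value is invented |
| Multiple imputation by MCMC, ITT (SAP 10.1) | Of the listed predictors (four baseline MNREAD measures and age), only age | Week 48 MRS is drawn and, under joint imputation, so are the baseline measures, extrapolated below the ages tested |
| Tipping point (SAP 10.1) | Endpoint missing | The child is assigned the worst or best observed change, then each step in between |

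**2. Does the tipping-point fill reach the p-value?** SAP 10.1 fills the change, is silent on filling baseline MRS, and does not name the model.
- With the SAP 7.7 ANCOVA, rows without a baseline still drop. In a 24-subject check with 6 missing baselines and the outcome filled, the model used 18 rows.
- With an unadjusted t-test the rows stay. For 6 of 24 untested and a true effect of 1.06 SD, the simulated mean estimate runs from -0.22 SD at the worst fill to 1.82 SD at the best.

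Two programmers following the text could therefore report different analyses.

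**3. Power by number tested.** Inputs: 2:1 allocation (SAP 2.4), two-sided 0.05, effect sizes d = 0.85 and 1.06 (Protocol 11.1). Two-sample t-test with df = n1 + n2 - 2 and noncentrality d / sqrt(1/n1 + 1/n2).

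The plan's own figure first. At 24:12, sqrt(1/24 + 1/12) = 0.354, so the noncentrality is 0.85/0.354 = 2.40 and 1.06/0.354 = 3.00. Power is 64.7% and 83.0%, not the stated 60% and 80%. At 22:11 it is 60.6% and 79.4%, so the stated figures match about 33 evaluable subjects. That would be a loss of 3/36 = 8%, which the documents do not state.

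The documents give no age mix, so the number tested is an assumption, as is 2:1 holding among those tested (the strata divide at age 10, not at ability to read).

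| Tested | Split | Example | Power at 0.85 | Power at 1.06 | Effect with 80% power |
|---|---|---|---|---|---|
| 36 | 24:12 | all of 36 | 65% | 83% | 1.02 SD |
| 27 | 18:9 | 27/36 = 75% | 52% | 70% | 1.19 SD |
| 24 | 16:8 | all of 24, or 24/36 = 67% | 47% | 65% | 1.27 SD |
| 18 | 12:6 | 18/24 = 75%, or 18/36 = 50% | 36% | 51% | 1.49 SD |

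**The case against.** **The primary analysis is safe.** This stands. LOCF and the ANCOVA cannot use an untested child, so the primary p-value and the gatekeeping in SAP 7.8 are unchanged. A reader might infer that the ITT rules put invented reading speeds into the primary result. They do not; the exposure is in the two sensitivity analyses.

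**Safeguards exist.** SAP 7.7 requires reasons for missingness to be reported and results with and without imputation to be compared. SAP 9 promises efficacy tables for the supportive set as well. These would let a careful reader see the problem, but they do not correct the rules. The supportive set is also not the right one for imputation: by requiring a post-baseline value it removes a tested subject who leaves without one, who is exactly the dropout to be imputed.

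**Untested children might seem to dilute the imputed effect.** For 3, 6 or 8 of 24 untested and a true effect of 1.06 SD, simulation gives about 0.94, 0.78 and 0.68 SD under multiple imputation, simplified to age as the predictor. But dropouts of tested ages give nearly the same (0.91, 0.79, 0.70), and adding treatment arm to the imputation model restores about 1.06. The cause is the absence of arm from the SAP's predictor list: imputed rows carry no treatment difference, so the effect is roughly 1.06 times the observed fraction (1.06 x 21/24 = 0.93; x 18/24 = 0.80; x 16/24 = 0.71). Untested children only raise the missing fraction.

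**The tipping point might seem bound to fail.** With 6 of 24 filled and an unadjusted test, no simulated trial was significant at the most adverse step. That follows from the number filled, whatever the reason for missingness, and SAP 10.1 asks only that the tipping step be noted.

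**The result might seem confined to ages 8 and over.** The age rule is permissive. A younger child may be tested, and an older one unable to read the chart also drops out.

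**The power statement might seem to assume that all 36 are tested.** The stated figures fit about 33, so that inference fails. No document says what the allowance is for.

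**Conclusion.** The point holds for the two sensitivity analyses and for the population label. As written, multiple imputation would draw baseline and Week 48 reading speeds for children never tested, from age alone. The tipping point would assign them best or worst changes, with an effect on the p-value that depends on an unstated choice of model and baseline. The primary LOCF/ANCOVA estimate is not distorted, but it describes subjects able to complete MNREAD at Day 1, mostly about 8 or older, and not the ITT set named as primary.

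The size cannot be fixed from the documents, because the number under 8 is not given and could be zero. If a quarter of subjects were untested and 2:1 held, power at 0.85 and 1.06 would be 52% and 70% for 36 enrolled, and 36% and 51% for the reduced 24.

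**What to change.** Before unmasking, amend the SAP as follows.

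1. Define an MNREAD analysis set: randomised, dosed subjects with a valid Day 1 binocular MNREAD value, analysed as randomised. Use the measured value and not an age cut, which would discard valid data from younger readers. Make this the primary set for MRS and the other MNREAD endpoints.
2. Limit LOCF, multiple imputation and the tipping point to that set, and name the model that produces the tipping-point p-values.
3. State in the SAP and the study report that MNREAD conclusions apply to that set, and report how many subjects were untested because of age or inability to read.
4. Replace the power sentence for MNREAD endpoints with power by number tested, as tabulated above, and reconcile the 36 subjects in SAP 2.4 and 7.1 with the 24 in SAP 2.5.

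The absence of treatment arm from the imputation predictors is a separate matter that these changes do not cure.

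The cost is SAP wording only, with no new data. The downside is a smaller stated sample size and less favourable power for the MNREAD endpoints. If left until after unmasking, the choice of set would be post hoc.

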### 8.3.16 Slit-Lamp Examination and Macro Photography

Slit lamp examination and macro photography will be performed on the lids, conjunctiva, limbus, cornea, anterior chamber, vitreous, and lens without pupil dilation. The Reading Center manual should be referenced for detailed instructions regarding macro photography.

Slit lamp examination (without pupil dilation) will be done for both eyes of the subjects for this study. Both the Haag-Streit and Zeiss slit lamp biomicroscopes are acceptable for study use and it is at the Investigator's discretion which manufacturer's brand will be used during the study; however, the same slit lamp biomicroscope must be used for assessing the anterior segment for all subjects enrolled and for all study visits throughout the trial.

It is recommended that the slit lamp examinations for an individual subject be performed by the same personnel using the same slit lamp for each study visit.

### **8.3.17 Fundus Examination and Photography**

Fundus examination and photography should be performed after testing visual acuity, slit lamp examination and macro photography.

A fundus exam will be performed of the retina, macula, and choroid. The largest cup-to-disc ratio measured should be entered on to the electronic case report form (eCRF). The Reading Center manual should be referenced for detailed instructions regarding fundus photography.

### **8.3.18 Optical Coherence Tomography**

Optical Coherence Tomography will be performed. The Reading Center manual should be referenced for detailed instructions.

### **8.3.19 Humphrey Visual Field**

Vision field testing will be performed by a Duke certified study technician. Humphrey visual field will be assessed. The Reading Center manual should be referenced for detailed instructions.

### **8.3.20 Ophthalmoscopy**

Ophthalmoscopic examination of the fundus will be performed using an indirect binocular ophthalmoscope. The largest cup to disc ratio measured should be entered on to the eCRF for each eye. Any abnormalities of the macula, vessels, periphery and disc are to be recorded. The study manual should be referenced for detailed instructions.

### **8.3.21 Best Corrected Visual Acuity (BCVA) and Refraction**

BCVA and refraction will be assessed using the Early Treatment Diabetic Retinopathy Study (ETDRS).

Refraction and testing of BCVA must be performed before the subject's eyes are dilated and prior to fundus photography and OCT imaging. Manifest refraction must precede the BCVA testing. For this study, it is estimated that children at the age of 6 or older will be able to be tested with a subjective refraction and ETDRS charts.

Age-appropriate alternative visual acuity chart (e.g., LEA symbols) will be used for any subject under the age of 6; however, the same chart should be used throughout the duration of the study.

The study manual should be referenced for detailed instructions.

[REDACTED]

- [REDACTED]
- [REDACTED]

[REDACTED]

[REDACTED]

[REDACTED]

[REDACTED]

- [REDACTED]
- [REDACTED]

[REDACTED]

[REDACTED]

[REDACTED]

[REDACTED]

[REDACTED]

[REDACTED]

[REDACTED]

## 9 ADVERSE EVENT ASSESSMENTS

### 9.1 Adverse Event Definitions

#### 9.1.1 Adverse Events

An adverse event is any untoward medical occurrence associated with the use of a drug (investigational medicinal product) in humans, whether or not it is considered related to the drug. An adverse event can therefore be any unfavorable and unintended sign (including an abnormal laboratory finding), symptom, or disease in a study subject who is administered study drug in this study.

For this protocol, untoward medical occurrences that should be reported as adverse events include the following:

- All adverse events that are suspected or are not suspected to be due to study drug.
- Overdose (administration of a study drug dose >4 times the intended total daily dose level for this protocol [ $>160$  mg/kg/day]) of study drug.
- All reactions from medication misuse, abuse, withdrawal, sensitivity, or toxicity.
- All reactions that result from medication errors or uses of the study drug outside what is described in the protocol.
- Apparently unrelated illnesses, including the worsening of a preexisting illness.
- Injury or accidents. Note that if a medical condition is known to have caused the injury or accident (a fall secondary to dizziness), the medical condition (dizziness) and the accident (fall) should be reported as two separate adverse events. The outcome of the accident (hip fracture secondary to the fall) should be recorded in source documents.
- Abnormalities in physiological testing or physical examination findings that require clinical intervention or further investigation (beyond ordering a repeat [confirmatory] test).
- Laboratory abnormalities that require clinical intervention or further investigation (beyond ordering a repeat [confirmatory] test) unless they are associated with an already reported clinical event. Laboratory abnormalities associated with a clinical event (e.g., elevated liver enzymes in a subject with jaundice) should be captured in the source documents. Laboratory abnormalities not requiring clinical intervention or further investigation will be captured as part of overall laboratory monitoring and should not be reported as adverse events.
- A pre-existing condition (e.g., allergic rhinitis) must be noted on the appropriate eCRF for Visit 1 but should not be reported as an adverse event unless the condition worsens, or episodes increase in frequency during the adverse event reporting period. Diagnostic and therapeutic non-invasive and invasive procedures, such as surgery, should not be reported as adverse events. However, the medical condition for which the procedure was performed should be reported if it meets the definition of an adverse event. For example, an acute appendicitis that begins during the adverse event reporting period should be reported as the adverse

event and the resulting appendectomy should be recorded in the source documents. If a surgical procedure was planned prior to entry into the study, and the surgery is not performed because of a worsening of a baseline condition, this should not be reported as an adverse event. Note that, as described in Section 9.1.2, any inpatient hospitalization occurring as the consequence of an adverse event during the study period should be reported as an SAE.

Each adverse event is to be classified as serious or non-serious by the investigator using medical and scientific judgment.

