## **9.3 Adverse Event Recording**

All adverse events (both serious and non-serious) that occur in subjects during the adverse event reporting period must be recorded, whether or not the event is considered drug related. In addition, any known untoward event that occurs subsequent to the adverse event reporting period that the investigator assesses as possibly related to the investigational drug/product should also be recorded as an adverse event.

All adverse events are to be recorded in the source documents and on the eCRF using concise medical terminology; whenever possible terms contained in the Medical Dictionary for Regulatory Activities (MedDRA) should be employed. In addition, the following information should be recorded:

- Indication of whether the event is serious or non-serious (see Section 9.1.2)
- Relationship to study drug (see Section 9.4)
- Severity of the event (see Section 9.5)
- Onset date
- Resolution date, or date of death
- Action taken
- Outcome of the event

Classification of the event as serious or non-serious determines the reporting procedures to be followed.

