5 DEFINITIONS

Adverse Event

An adverse event (AE) is any untoward medical occurrence associated with the use of a drug (investigational medicinal product) in humans, whether or not it is considered related to the drug. An adverse event can therefore be any unfavorable and unintended sign (including an abnormal laboratory finding), symptom, or disease in a study subject who is administered study drug in this study. A specific list of occurrences that should be reported as AEs is provided in section 9.1.1 of the study protocol. Subjects must be followed for adverse events for at least 28 days after the last dose of ataluren administration, or until any drug-related adverse events and/or ongoing serious adverse events (SAEs) have resolved or become stable, whichever is later. Any event that starts within 35 days (to account for visit window) after last dose of ataluren will be summarized.

Adverse events will be graded for severity using Common Terminology Criteria for Adverse Events (CTCAE) Version 4 grading, where 1=Mild, 2=Moderate, 3=Severe, 4=Life-threatening, and 5=Fatal.

Relationship to study treatment will be coded using the following categories: Unrelated, Unlikely related, Possibly related, and Probably related. In summaries where relatedness is dichotomized to related or not, Unrelated and Unlikely related will be classified as not related and Possibly related and Probably related will be classified as related.

Serious Adverse Event:

A serious adverse event is defined as an adverse event that

- Results in death
- Is life-threatening (patient is at immediate risk of death from the event as it occurred)
- Requires in-patient hospitalization (formal admission to a hospital for medical reasons) or prolongation of existing hospitalization
- Results in persistent or significant disability/incapacity
- Results in a congenital anomaly/birth defect

Treatment-Emergent AE:

A TEAE is any AE that begins or increases in severity after the initial dose of study drug and within 5 weeks of the last dose of study drug.

Age

Subject's age is defined as from date of birth to randomization date. The formula used is (randomization date – date of birth+1) / 365.25.

Ataluren Exposure

The duration of exposure to ataluren treatment is defined as the last dose date minus the first dose date + 1 day.

Baseline

For any variable, unless otherwise defined, baseline is the last assessment taken prior to the first study drug administration.

Change from Baseline

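### Protocol 9.1.1 lists injuries as reportable adverse events, but its worked example sends the injury caused by an accident to source documents, so injuries may be missing under their own term.

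*Protocol*

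**What the plan says.** Protocol 9.1.1 lists occurrences to be reported as adverse events. One bullet opens: "Injury or accidents. Note that if a medical condition is known to have caused the injury or accident (a fall secondary to dizziness". For that case it continues: "the medical condition (dizziness) and the accident (fall) should be reported as two separate adverse events". It then adds: "The outcome of the accident (hip fracture secondary to the fall) should be recorded in source documents".

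Protocol 9.3 sets the general rule: "All adverse events (both serious and non-serious) that occur in subjects during the adverse event reporting period must be recorded". The same section says that adverse events go into the source documents and onto the eCRF.

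Protocol 11.8.1 takes adverse events from the eCRF adverse event pages and tabulates them by System Organ Class and Preferred Term, by severity, and in a separate ocular category. SAP 7.5.1 plans the same kinds of table. SAP 5 adds no rule on injuries and defers to the protocol: "A specific list of occurrences that should be reported as AEs is provided in section 9.1.1 of the study protocol".

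**The concern.** A fracture is a new medical condition and meets the general definition that opens 9.1.1. In the example it is the most serious harm in the chain, yet it is the one item not counted as an event. If a site applies the example as written, the coded events are the dizziness and the fall. The harm itself is neither coded nor graded under its own term.

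Safety is a secondary objective (Protocol 3.1.2), and Protocol 13.2.3.11 promises particular attention to ocular findings. The subjects have impaired vision and may be as young as 2 years, so accidental injury is a plausible safety outcome here. A safety table that shows a fall but not its consequence understates what happened to the subject.

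**Working it through.** The plan has no figure to reproduce, so the check is a comparison of text, followed by a small calculation of scale.

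1. **What the example counts.** It names three things: dizziness, fall and hip fracture. It counts two adverse events, the dizziness and the fall. The fracture is in neither.

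2. **What the last sentence adds.** Under 9.3 every adverse event already goes to source documents and the eCRF. If the fracture were an adverse event, telling the site to put it in source documents would add nothing. The sentence has a function only if the fracture is not reported separately.

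3. **How 9.1.1 uses the phrase elsewhere.** On laboratory findings tied to a clinical event: "Laboratory abnormalities associated with a clinical event (e.g., elevated liver enzymes in a subject with jaundice) should be captured in the source documents". On a procedure: "the resulting appendectomy should be recorded in the source documents". In both, source documents stand in place of a separate adverse event report. Those two items are a supporting finding and a procedure. A fracture is neither.

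4. **The conflict.** The bullet itself names injury as reportable, and 9.3 requires all adverse events to be recorded. The example points the other way. A site is likely to follow a specific example over a general definition.

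5. **Whether other provisions close the gap.**
   - Hospitalization makes the event serious (9.1.1 and 9.1.2), but the serious event can still carry the term fall, and 9.9 asks for the same term on both forms. Emergency room observation under 24 hours is not serious (9.1.2).
   - For serious events, Table 6 sends source documents to the sponsor. For non-serious events it asks only for eCRFs.
   - The bullet on examination findings that need intervention or further investigation could bring in a treated injury, but it is general, while the accident example names the case.
   - Ocular adverse events are assessed at each scheduled visit (8.3.12), but that section does not say whether an injury from an accident is its own event.

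   Each route may capture some injuries. None reliably puts the injury under its own term.

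6. **Scale of one missing record.** Assume exact 2:1 allocation with every subject dosed.
   - With 24 subjects (SAP 2.5) the arms are 24 × 2/3 = 16 and 24 × 1/3 = 8. One subject is 1/16 = 6.25% or 1/8 = 12.5% of an arm.
   - With 36 subjects (Protocol 11.1, SAP 7.1) the arms are 24 and 12. One subject is 1/24 = 4.2% or 1/12 = 8.3%.

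   This shows what one omission does to a Stage 1 row. It does not estimate how many omissions there will be.

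**The case against.** The best case for leaving the text alone is this. The sentence does not confine the injury to source documents and does not say that it is not an adverse event. Where 9.1.1 means to exclude something, as with laboratory abnormalities needing no action or with procedures, it says so outright. Injury is in the bullet's opening words. The note begins with accidents caused by a medical condition, so a child who trips and breaks an arm falls outside it on a natural reading. The accident and its cause are still counted, the eCRF also holds outcome and treatment required, and serious events get tables or narratives under SAP 7.5.1. Adverse events are not tested statistically (Protocol 11.8).

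Much of this stands, and it limits the point. A reader might infer that accident injuries go to source documents alone and can never reach the adverse event tables. The documents do not support that, because the wording is not exclusive and the routes in the working exist. A reader might also infer that eye injuries are known to be lost. The only example is a hip fracture, and ocular events are separately sought and tabulated, so an eye injury is affected only if a site extends the example to it.

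What the objection does not remove is the count of two, the redundancy of the sentence under 9.3 on any other reading, and the lack of a route that secures the injury's own term. Doubt over whether the sentence covers all accidents or only condition-caused ones is a further reason to rewrite it.

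**Conclusion.** The point holds as an internal inconsistency with a practical consequence. If the example is followed, an injury resulting from an accident may be missing under its own Preferred Term and severity grade, and from the ocular table if it is ocular. This applies at least to accidents caused by a medical condition.

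The conclusion assumes that sites follow the example over the general definition and that no other route brings the injury in under its own term. The number of subjects affected cannot be estimated, because the documents give no rate of falls, accidents or injuries, and any count would be the product of an assumed rate. Sample size, power, significance level and the efficacy analyses are unaffected. The change is worth making because this is a stated instruction rather than a missing detail, the arms are small, and the remedy is cheap.

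**What to change.** Replace the last sentence of the bullet in Protocol 9.1.1 with text such as: *The resulting injury (for example, a hip fracture) is entered on the adverse event eCRF as its own event, with its own severity grade and seriousness, in addition to the accident and any causal condition, in line with Section 9.3.* State that this applies to all accidents, whatever their cause. The SAP needs no separate rule, since SAP 5 refers to the protocol list.

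For accidents already recorded, query sites once for linked injuries held only in source documents.

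The cost is one sentence, a site memo, a limited query and a few more adverse event records. Protocol 11.8.1 counts subjects rather than events, so a subject already counted for a fall adds nothing to the count of subjects with any adverse event. Only the Preferred Term, severity, seriousness and ocular rows can change.
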